QC Quality Control

SAE Serious Adverse Event/Serious Adverse Experience

SOP Standard Operating Procedure

SRP Scaling and Root Planing
UP Unanticipated Problem

PROTOCOL SUMMARY

Title:

Shaping the Indications for Periodontal Adjunctive Antibiotics in Dental Practice: A PBRN Clinical Trial (PAAS)

Précis:

Periodontitis is a bacterial inflammatory disease and antibiotic use is being empirically used as part of its treatment. However, a clinical practice guideline on periodontal treatment adjuncts published in 2015 identified weak evidence on the use of systemic antibiotics and large heterogeneity across small scale studies, suggesting that larger pragmatic clinical trials would benefit clinical decision making. This will be a prospective, randomized, placebo-controlled trial, stratified by practice and practitioner. The study will investigate the effectiveness of adjunctive antibiotics as adjunct to scaling and root planing (SRP) compared to SRP with placebo for the treatment of generalized stage II-III, grades A-C periodontitis in approximately 544 patient participants from about 34 National Dental PBRN practices. Periodontal data will be collected at baseline, re-evaluation (6 weeks), and final (12 month) study visits. Changes in periodontal clinical and patient-reported outcomes will be assessed to determine the effectiveness of SRP plus adjunctive systemic Amoxicillin / Metronidazole antibiotics (AMXM) versus SRP with Placebo.

Objectives and Outcomes:

Primary: The primary objective will assess the effectiveness of SRP plus adjunctive antibiotics compared to SRP with placebo in periodontitis individuals from baseline to 6 weeks and 12 months following non-surgical periodontal therapy (NSPT) as determined by changes in site-level periodontal probing depth (PD).

Secondary: To assess changes in: i) gingival inflammation (measured by bleeding on probing (BoP)), ii) periodontal tissue attachment (measured by clinical attachment level (CAL)), iii) reduction in diseased sites (measured by remaining sites with maximum probing depth ≥5 mm), and iv) disease remission (measured by number of participants with ≤4 sites with PD≥ 5mm); comparing SRP plus AMXM to SRP with a placebo adjunctive in periodontitis individuals from baseline to reevaluation (6 weeks) to final 12 month study visit following intervention. The patient-reported impact of periodontal treatment (measured by the Oral Health Impact Profile-5 (OHIP-5)) and treatment-related adverse events between groups will also be assessed.

Population: The sample size will be a target of approximately 544 patient

participants enrolled from approximately 34 National Dental PBRN practices. All patient participants are indicated to receive SRP and have been diagnosed with periodontitis

stages II-III, grades A-C.

Phase or Stage: Phase III Clinical Trial

Number of Sites: Approximately 34 PBRN practitioner locations from across the

Western, South Central, and Southwestern nodes.

Description of Intervention:

The intervention will involve either SRP, which is considered the standard of care treatment for debriding root surfaces, in conjunction with 500 mg Amoxicillin and 500mg Metronidazole orally every 8 hours (q8h) for ten days following SRP or SRP

with placebo.

Study Duration: 34 months (including data system build and data analysis)

Participation Duration:

Approximately 12 months (range 10-15 months) - for patient

[figure not shown]
participants, from baseline to final study visit.

Estimated Time to Complete

Enrollment:

Approximately 6-8 months for patient participant enrollment.

Schematic of Study Design:

2 INTRODUCTION: BACKGROUND INFORMATION AND SCIENTIFIC RATIONALE

2.1 Background Information

Periodontitis is among the most prevalent causes of years lived with disability among adults worldwide (GDB Collaborators 2020). Periodontitis is a bacterial inflammatory disease that has been reported to affect nearly 40% of Americans aged 30 years or older (GDB Collaborators 2020). If left untreated, periodontitis can lead to tooth loss and patient-perceived morbidity (Eke et al. 2018). Historically, antibiotic use has been an integral part of periodontal disease treatment. However, antibiotic stewardship calls for optimizing antibiotic prescribing to effectively treat infections, reduce antibiotic misuse, and prevent the development of antibiotic-resistant microbial strains (Dinsbach 2012, Doron & Davidson 2011, Sabtu et al. 2015). Since 2015, the American Dental Association (ADA) developed evidence-based guidelines limiting circumstances for prophylactic antibiotic use in dental practice (Sollecito et al. 2015, Lockhart et al. 2019); however, evidence regarding antibiotic use in the treatment of periodontal infections is considered weak because of substantial inconsistencies across small scale trials (Smiley et al. 2015). Further, existing trials are underpowered to assess the effects of disease- and patient-related factors to adjunctive antibiotic benefit, therefore, dentists are left to decide when adjunctive antibiotics are indicated, and which dental patients need them to achieve periodontal health (Smiley et al. 2015). In the context of periodontitis treatment, a biological rationale exists to support adjunctive antibiotic use to reduce periodontal pathogenic bacteria, but clinical trials assessing adjunctive antibiotic effectiveness have presented varying results depending on the study, sample population and disease characteristics (Hafajee et al. 2003, Hafajee et al. 2007, Teughels et al. 2020). Nonetheless, data from academic studies suggest that adjunctive systemic antibiotics may be beneficial for certain populations only, as the biological response to treatment is highly variable across individuals (Smiley et al. 2015). This marked variability warrants the identification of person and/or diseaserelated characteristics that are linked to maximum benefit from adjunctive antibiotic treatment. Consequently, guidelines may be established with tailored indications for their use with the goal of minimizing antibiotic misuse in periodontal treatment to avoid development of antibiotic resistance while optimizing outcomes (Garcia et al. 2013).

Persons diagnosed with periodontitis undergo non-surgical periodontal therapy (NSPT), a therapeutic regime that may include procedures such as scaling and root planing (SRP), adjunctive antibiotic prescription, and/or other antimicrobial treatments. Specifically, SRP alone is the most commonly employed form of NSPT and is considered standard of care treatment for periodontal disease (Badersten et al. 1981, Badersten et al. 1984, Cercek et al. 1983, Smiley et al. 2015). SRP entails the mechanical debridement of the root surfaces of teeth as part of periodontal treatment. The effectiveness of SRP is well documented, and a 2015 meta-analysis suggested that it leads to approximately a 0.5 mm average improvement in clinical attachment (Smiley et al. 2015). Nonetheless, in certain indications, such as in severe or aggressive periodontitis cases there may be a benefit to adjunctive systemic antibiotic administration in conjunction with SRP based on small-scale clinical trials (Bechara

Andere et al. 2018, Berglundh et al. 1998, Drisko 2001, Pihlstrom et al. 1984). These indications, however, are not compatible with the latest periodontitis classification system (Tonetti et al. 2018). Therefore, a gap in clinical translation exists.

Amoxicillin is a broad spectrum antibacterial of the penicillin family commonly used in the treatment of oral soft tissue infection. Metronidazole is also an antibiotic with higher efficacy for anaerobic bacteria associated with periodontal disease. In conjunction, AMXM have become the most used antibiotic adjunct in the treatment of chronic periodontal disease (Garcia Canas et al. 2015, Smiley et al. 2015). In the present study, the test arm will receive SRP plus adjunctive systemic Amoxicillin / Metronidazole antibiotics (AMXM group); the control arm will receive SRP plus Placebo (Placebo group) without any active adjuncts.

2.2 Rationale

Infection-related mortality caused by antibiotic-resistant bacteria has emerged as a leading cause of death for people of all ages, therefore appropriation of antibiotic usage only when they may be effective based on evidence-based clinical practice guidelines, is becoming a priority across medical disciplines (Doron et al. 2011). In 2019, the ADA developed evidence-based guidelines limiting circumstances for prophylactic antibiotic use for the management of endodontic infections (Lockhart et al. 2019). Nonetheless, a clinical practice guideline on periodontal treatment adjuncts published in 2015 identified weak evidence on the use of systemic antibiotics and large heterogeneity across small scale studies, suggesting that larger pragmatic clinical trials would benefit clinical decision making (Smiley et al. 2015, Oberoi et al. 2015). Two main limitations exist that impede the development of evidence-based guidelines with high level of certainty on the use of adjunctive antibiotics in the treatment of periodontitis. Firstly, existing trials assessing adjunctive antibiotic effectiveness have small sample sizes, primarily sampling from university clinic-based populations that may not fully reflect clinical practice conditions (Boia et al. 2019, Jentsch et al. 2016). Secondly, existing periodontal antibiotic effectiveness trials are based on older periodontitis classification systems that have now been superseded and were not designed to capture individual variability under the "umbrella" disease term of "periodontitis" (Tonetti et al. 2018). The current classification system of periodontitis was developed in 2017 at the World Workshop of Periodontics and it has been implemented in practice since 2018 (Tonetti et al. 2018). This system, now the only system recognized by the ADA and the American Academy of Periodontology (AAP), introduced an evidence-based periodontitis staging and grading system (Tonetti et al. 2018). Stages and grades of periodontitis capture individual variability within periodontitis phenotypes better and have paved the way for more personalized dental care (Papapanou et al. 2018).

To address limitations in evidence pertaining to adjunctive antibiotic use as part of NSPT, the study objective is to assess the effectiveness of systemic AMXM combination antibiotics as an adjunct to SRP (AMXM group) vs. SRP alone (Placebo group) in periodontal patients with Stages II-III, Grade A-C periodontitis who receive care in clinical practices within the National Dental PBRN. In brief, patient participants in

the AMXM group will receive a loading dose of Amoxicillin 500mg and Metronidazole 500mg followed by a self-administered dose (500mg) of the two drugs every 8 hours (qh8) for 10 days. This regimen was employed in a recent periodontitis clinical trial of forty-two adult patient participants and demonstrated a high safety profile with no drug-related adverse events (Ramón Gómez-Sandoval et al. 2020). Additionally, the present study will include effect modification analyses for sample subpopulations of interest, such as smokers versus non-smokers and groups with different rates of disease progression from more chronic (Grade A) to more aggressive (Grade C), in order to assess whether there may be benefit to adjunctive antibiotics targeted to specific populations.

2.3 Potential Risks and Benefits

2.3.1 Potential Risks

Risks related to SRP

SRP is a non-surgical procedure that involves mechanical debridement of the roots of the teeth using dental instruments. This procedure may lead to root sensitivity, which may be transient or long term. It can also lead to gum recession and exposure of part of the root in the oral cavity. A periodontal abscess may form within days after SRP, which may cause pain and may require additional dental procedures for drainage. Patient participants will contact their dental practitioner if any adverse event including post-procedural pain, swelling, trauma, or bleeding has occurred.

Risks related to Amoxicillin and Metronidazole antibiotic intake

Antibiotic intake is associated with gastrointestinal adverse events such as fungal infections in the mouth or elsewhere in the body, nausea, and/or diarrhea. Women taking broad spectrum antibiotics are at increased risk of developing a yeast infection due to a reduction in healthy vaginal bacteria. Use of antibiotics may decrease the efficacy of hormonal contraceptives (birth control); use of a secondary method of birth control should be encouraged. It can also lead to adverse events including allergic / anaphylactic reactions. The possibility of adverse events (allergic reaction) will be mitigated with exclusion criteria that eliminate patients with a history of allergy or adverse effects associated with penicillin, Amoxicillin, or Metronidazole families of antibiotics

Patient participants will also have a thorough review of their medication history to prevent adverse interactions with study medications.

After being administered antibiotics, patient participants will be monitored while in the office until treatment completion and discharge to determine if any adverse reaction has occurred. Patient participants who experience allergic or other adverse reactions due to study medications will be referred for immediate medical care as needed. The event of experiencing any severe adverse events with subsequent antibiotic doses is rare, and if that happens, the patients will call their dental provider. The research team will not routinely follow-up with the participants with a text or phone call. Drug-related adverse reactions will be a

reason for discontinuation of the drug as detailed in section 6. All prescribed treatments (outside of the study) will continue as planned.

Risks related to Placebo intake

This procedure (SRP) is routinely done using both methods tested in this trial: with or without antibiotics. Therefore, no physical risk is expected if the patients receive a placebo, as SRP is often done without antibiotics in clinical settings.

Risks related to subgingival plaque specimen collection

The collection of subgingival plaque for future microbiome analysis using paper points is minimally invasive since plaque is usually present and manipulated during SRP. No risks are expected beyond mild discomfort upon paper point insertion in the sulcus. All practitioners will undergo training on obtaining plaque samples with gentle pressure during insertion of paper points to mitigate risk. Samples will be kept in the study's repository in a -20 degrees Celsius freezer, which will include a temperature sensor with alarm to minimize any risk of sample loss due to bad storage.

Risks related to loss of confidentiality

As with any study, there is the potential for loss of confidentiality; however, appropriate precautions will be taken to mitigate this risk. These precautions include the use of unique study codes for patient participants, password-protected computers, and secure networks for data storage. Compliance with all Institutional Review Board (IRB) regulations concerning data collection, data storage, and data destruction will be strictly observed. Data will only be accessible to research study personnel and will be stored and coded according to Office for Human Research Protections (OHRP) guidelines.

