9 ASSESSMENT OF SAFETY

9.1 Specification of Safety Parameters

Safety monitoring for this study will focus on unanticipated problems (UPs) involving risks to study patient participants, including UPs that meet the definition of a serious adverse event (SAE). The practitioner will inform the patient participants about the risk and nature of adverse events during the consent process. In case of a SAE (anaphylactic reaction to antibiotics), the patient participants will be instructed during the consent process to call 911. The practitioner will also exclude patients if they meet the following exclusion criteria to minimize the risk of adverse events:

- 1. Potential participant has a known drug allergy to antibiotics or anesthetics.
- Potential participant currently uses medications that may cause adverse effects with Amoxicillin/Metronidazole (AMXM) such as disulfiram, warfarin, oral contraceptives

Patient participants will contact their practitioner in case of an AE and the practitioner will address any patient participant needs or concerns regarding the AE. In addition, the practitioner will record adverse events (AEs) using a designated form and inform the node coordinator. The PI will monitor these events to grade severity, relationship to the study intervention and procedures, and assess whether the nature, severity, or frequency is unexpected. Safety data will be collected at all study visits through solicitation of adverse events from patient participants. Practitioners will record safety data on the Adverse Events eCRF and any questions should be directed to the Node coordinator.

Safety events will be recorded and reported into the National Dental PBRN safety event reporting system maintained by the NCC. Study PI will be informed via the safety event system when events are reported.

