9.3.2 Expectedness

The Study PI and/or study-appointed, clinically/medically responsible individual will determine whether an AE is expected or unexpected. An AE will be considered unexpected if the nature, severity, or frequency of the event is not consistent with the risk information previously described for the intervention.

The following are expected AEs that may occur with this research study:

- a. Post procedural tooth sensitivity: Sensitivity is defined as specific or generalized tooth sensitivity or pain to air, temperature, or pressure that is a unique experience directly related to the previous procedure and may become apparent when local anesthesia is cleared.
- b. Post procedural pain: This post-procedural pain is related to tissue discomfort or pain directly related to the previous procedure and may become apparent when local anesthesia is cleared.

- c. Periodontal abscess: post-procedural deep pocket abscess can occur where epithelial (surface gingival) heals more quickly than deeper periodontal tissue causing a stricture (collar) to tighten around the tooth trapping sulcular fluid and building up pressure.
- d. Nausea associated with antibiotic use: This can occur within several hours of the first dose of medication and may continue during dosing.
- e. Allergic reaction: rash or itching
- f. Allergic reaction: difficulties breathing

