9.3.3 Severity of Event

The following scale will be used to grade adverse events:

- 1. Mild: no intervention required; no impact on activities of daily living (ADL)
- 2. Moderate: minimal, local, or non-invasive intervention indicated; moderate impact on ADL
- 3. Severe: significant symptoms requiring invasive intervention; subject seeks medical attention, needs major assistance with ADL

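### For a serious or anaphylactic reaction to a dose taken at home, protocol sections 2.3.1 and 9.1 name different first contacts

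*Protocol*

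**What the plan says.** Section 2.3.1 of the protocol, under the risks of the study antibiotics, names the reaction at issue: "It can also lead to adverse events including allergic / anaphylactic reactions". After describing observation in the office until discharge, it turns to any severe event after later doses, calls it rare, and says: "if that happens, the patients will call their dental provider". It gives no other contact for a participant who is at home.

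Section 9.1 gives a different route: "In case of a SAE (anaphylactic reaction to antibiotics), the patient participants will be instructed during the consent process to call 911". Its next paragraph adds the general rule: "Patient participants will contact their practitioner in case of an AE and the practitioner will address any patient participant needs or concerns regarding the AE".

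Section 9.3.2 lists "Allergic reaction: difficulties breathing" among the expected adverse events, so the protocol foresees a reaction of this kind. Section 9.3.3 defines the top severity grade as "Severe: significant symptoms requiring invasive intervention; subject seeks medical attention, needs major assistance with ADL". Section 9.1.3 defines seriousness separately, by outcome, with threat to life as one criterion.

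**The concern.** After the loading dose the participant takes the study drug unsupervised, and the protocol foresees allergic reactions. For the most dangerous of them, one section sends the participant to the dental provider and another to emergency services. A practice or consent discussion that follows section 2.3.1 could convey something different from one that follows section 9.1. This is a rule for participant safety, so it should read the same wherever it appears.

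**Working it through.** **Setting.** Sections 4.2 and 6.2 give two loading capsules from each bottle in the office, then one capsule from each bottle three times a day for ten days. Capsules per bottle: 2 + 3 × 10 = 32, which reproduces the figure in section 6.1.2. Home capsules: 32 − 2 = 30, or 30/32 = 93.75%. Section 2.2 words the loading dose as 500 mg of each drug. That is a separate inconsistency, and the scheduled home course is still 3 × 10 = 30. These figures show where the rule applies; they do not measure risk.

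**Severe against serious.** Severity (section 9.3.3) is a grade of intensity. Seriousness (section 9.1.3) depends on outcome. Section 2.3.1 covers any severe event after later doses; section 9.1 ties the 911 instruction to serious events. The bracketed mention of anaphylaxis in 9.1 can be read as an example of a serious event or as the only event meant. Anaphylaxis is covered on either reading.

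**Side by side.** Treating the dental provider of 2.3.1 and the practitioner of 9.1 as the same contact:

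| Reaction to a home dose | Section 2.3.1 | Section 9.1 | Agree? |
|---|---|---|---|
| Severe, not serious | dental provider | practitioner, under the general adverse event rule | yes |
| Severe and serious, anaphylaxis named | dental provider | 911, as told at consent | no |

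**Can the text settle the second row?** Neither section refers to the other, and neither gives an order or a threshold. Section 2.3.1 does say that participants who react are sent on for prompt medical care where needed. That sentence directly follows the one on observation in the office, and it does not say what a participant at home should do.

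**Who is affected.** The target is 34 practitioners × 16 = 544 participants, or 272 per arm. Section 5.4.2 states that the instructions for using the product are the same in both groups, and participants are blinded. The ambiguity therefore concerns about 544 participants, not only the 272 on active drug.

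**The case against.** The strongest reply is that the sections can be read together. Only 9.1 states what participants are told at consent; the sentence in 2.3.1 is part of a risk narrative and prescribes no consent wording. Severe and serious are defined separately, and the two contacts do not exclude each other: a participant could call 911 and then the practice. This narrows the point to the overlap but does not remove it. Section 2.3.1 speaks of any severe event, in the subsection that names anaphylaxis, without excluding serious reactions, and no section states a sequence.

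A reader might infer more than the protocol supports:

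- **That the participant's own instruction is the only safeguard after discharge.** Section 5.2 excludes known antibiotic allergy, section 6.3 provides for stopping the drug, and section 7.7 covers unscheduled visits. Appendix A schedules adverse event assessment at the optional second baseline visit and at the day-10 text. Section 7.3 describes that text only as a capsule count request and bottle reminder, and none of these tells a participant whom to call during a reaction, but they are safeguards.
- **That practices will give different instructions.** The consent form, training content and written medication instructions are not shown, so this is a possibility only.
- **That an event handled through 911 would escape the safety system.** Section 9.1 already has participants contact the practitioner for adverse events, and by section 9.1.2 these include serious ones. Section 9.2 requires an inquiry at every study visit.
- **That listing breathing difficulty as expected contradicts calling severe events rare.** In section 9.3.2 expectedness means consistency with the described risk information. It says nothing about frequency.

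**Conclusion.** The inconsistency is real and narrow. For a severe drug reaction at home that is also serious, with anaphylaxis as the named case, sections 2.3.1 and 9.1 give different contacts and no order between them. For severe but non-serious reactions they agree. The conclusion assumes that an anaphylactic reaction counts as severe in the sense of 2.3.1 and that the dental provider there is the practitioner of 9.1. It concerns about 544 blinded participants. The number of events cannot be estimated, because the protocol gives no rate and says only that severe events with later doses are rare. Sample size, power and type I error are untouched. The point deserves correction because the rule concerns participant safety and the change is small.

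**What to change.** Reconcile sections 2.3.1 and 9.1 to one consistent instruction for serious reactions at home, and cross-reference the two sections. Use the same wording in the consent discussion and in the written medication instructions that section 8.1 says are dispensed. Which contact or sequence to state is for the investigators to decide. No separate rule for notifying the practitioner is needed, since sections 9.1 and 9.2 largely cover it.

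The cost is a few lines of text and a check of the consent and instruction materials. Under section 15.2 a protocol amendment needs central IRB approval. No procedure, data item or analysis changes.
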